## Study Protocol

The proposed study is a repeated measures experimental design in which participants will complete prescreening measures and APD tests in both English (L2) and Spanish (L1). Participants' performance on APD tests will be compared between L1 and L2 to determine if the language used in the test materials impacts auditory processing performance.

Upon arrival participants will complete the consent process in which the PI will describe in detail all study procedures, risks and benefits of the study, and the lack of negative consequences should the participant choose to withdraw from the study or cease participation during data collection. Once the consent form has been signed, the participant will complete a basic hearing evaluation to ensure all inclusion criteria are met. This will include:

- Otoscopy - to ensure normal external ear anatomy and no visual abnormalities, infection, or damage are present in the external ear or eardrum
- Tympanometry - to assess middle ear health and function
- Air and bone conduction - to assess hearing sensitivity across a range of frequencies (i.e., octave frequencies from 250-8000 Hz)
- Speech recognition threshold (SRT) - to determine the lowest level at which the participant can recognize and repeat a two-syllable word accurately

If during the hearing evaluation a hearing loss is found, the participant will be appropriately counseled regarding the hearing loss and referred for diagnostic testing. These individuals will not qualify to participate in this study.

Language proficiency in both Spanish and English will be assessed via questionnaire and an online proficiency test offered by Transparent Language (<https://www.transparent.com/learn-spanish/proficiency-test.html>). These proficiency tests will assess grammar, vocabulary, and reading comprehension in each language. To be considered proficient in a given language, participants must score above 80% on the assessment (Mendel & Widner, 2016).

If a participant meets all inclusion criteria (normal results for all above-mentioned tests and below-specified demographics), auditory processing tests will be completed. Each participant will be tested twice, once in Spanish and once in English, using dichotic digits, competing words, and competing sentences (scoring sheets included). Descriptions of these tests are as follows:

- Dichotic digits. This test is a binaural integration task to assess the patient's ability to integrate information being presented to both ears. During this test, the participant will be presented with four numbers (1-10 excluding 7), two in each ear simultaneously. The participant will be asked to repeat all four numbers; the order of repetition is not important.
- Dichotic word listening test (DWLT). During this test, two words are presented, one in each ear. The participant is instructed to repeat the word presented at the target ear (specified in test instructions), while they ignore the word in the opposite ear. This is an assessment of the participant's ability to separate relevant information from unwanted, distractor information. The word presented in the target ear will be presented at a lower presentation level than the word presented in the opposite ear.

Title: Comparing central auditory processing performance in bilinguals using L1 vs. L2 materials

- Synthetic sentence identification (SSI) test. During this test, two complete sentences are presented, one in each ear. The participant is instructed to only repeat the sentence presented at the target ear (specified in test instructions), while they ignore the sentence in the opposite ear. The sentence in the target ear is presented at 35 dB SL, while the ignored sentence is presented at 50 dB SL. This assesses the participant's ability to separate information coming into both ears and the ability to ignore unwanted information.

The presentation of the Spanish and English test materials will be counterbalanced across participants to minimize fatigue and practice effects. Following completion of tests, the test results will be discussed with the patient. If any indication of hearing loss or auditory processing deficits are identified, the participant will be notified and appropriate recommendations for more thorough evaluations and treatment will be provided.

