## **Data Analysis**

Mixed linear regression models will be used to evaluate performance differences between L1 and L2 on APD assessments. Post-hoc adjustments will be used to correct for multiple comparisons. Correlations will also be conducted to investigate relationships between auditory processing performance and demographic variables including language proficiency.

Based on the proposed analyses, an a priori power analysis was conducted to estimate the required sample size. The power analysis (t-test estimates, 2-tailed,  $\alpha = 0.05$ , power = 0.90; G\*Power 3.1; Faul et al., 2007) revealed a sample size of 19 participants would be sufficient to detect large effect sizes ( $d = 0.8$ ), similar effects as reported in studies using similar paradigms (Desjardins et al., 2019; Lopez et al., 1997).

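### Does the study need a reverse-L1 group because the L1 versus L2 contrast is also a Spanish versus English contrast?

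*Combined protocol and SAP*

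**What the plan says.** The Study Protocol section describes a repeated measures design in which "participants will complete prescreening measures and APD tests in both English (L2) and Spanish (L1". On testing it says: "Each participant will be tested twice, once in Spanish and once in English, using dichotic digits, competing words, and competing sentences". The purpose of the comparison is "to determine if the language used in the test materials impacts auditory processing performance", and the running title is "Comparing central auditory processing performance in bilinguals using L1 vs. L2 materials".

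Order is handled as follows: "The presentation of the Spanish and English test materials will be counterbalanced across participants to minimize fatigue and practice effects". For dichotic digits one set is described, with no separate set for Spanish: "the participant will be presented with four numbers (1-10 excluding 7), two in each ear simultaneously".

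The Data Analysis section states: "Mixed linear regression models will be used to evaluate performance differences between L1 and L2 on APD assessments". It also plans correlations with demographic variables, including proficiency, and sizes the study at 19 for d = 0.8, two-sided alpha 0.05 and power 0.90.

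Eligibility depends on "normal results for all above-mentioned tests and below-specified demographics". Neither those demographics nor the scoring sheets are in the text available here, so their absence is not held against the plan.

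**The concern.** The heading and the model speak of L1 versus L2, but every participant described has Spanish as L1 and English as L2. Whatever makes the Spanish materials harder or easier than the English ones enters the contrast in full. Counterbalancing removes order effects and leaves this untouched. The proficiency correlations do not help either, because they do not vary which language is L1.

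The digit set gives a concrete reason for worry. All nine English number words left after dropping 7 have one syllable. In Spanish, five of the nine have two. In a task that presents digits at the same moment to both ears, a mismatch in word length could matter.

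At stake is the interpretation. A significant difference could be an L1 effect, a version effect or both. A null could be neither, two effects that cancel, or lack of power. More participants of the same kind would not resolve this.

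**Working it through.** **Inputs.** From Data Analysis: n = 19, d = 0.8, two-sided alpha 0.05, power 0.90. From Study Protocol: Spanish = L1, English = L2, each participant tested in both languages, digit set 1–10 without 7. Assumptions: d is the mean paired difference divided by its SD, and that SD is set to 1.

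**1. The plan's own figure.** For a paired t-test, the noncentrality is d√n with n − 1 df.
- n = 18: 0.8 × √18 = 3.39, power 0.892.
- n = 19: 0.8 × √19 = 3.49, power 0.909.

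So 19 is the smallest n with 90% power, and the stated figure is reproduced.

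**2. Is the confounding real?** With 19 Spanish-L1 participants, participant effects (19 columns) plus version and L1 status make 21 columns. The rank is 20, because version and L1 status are the same information. If L1 status had no effect, a pure version difference of 0.3, 0.5 or 0.8 SD (assumed range) would be significant with probability 0.24, 0.54 or 0.91.

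**3. The digits.** Spanish syllables for 1, 2, 3, 4, 5, 6, 8, 9, 10 are 2, 1, 1, 2, 2, 1, 2, 2, 1, with sum 14 and mean 14/9 = 1.56. In English all are 1. Pairs of unequal length: 5 × 4 = 20 of 36 in Spanish, 0 in English. If the four digits of an item differ and are drawn evenly, 79% of Spanish items contain an unequal simultaneous pair. But 36 − 20 = 16 Spanish pairs are equal in length, so a list built with matched pairs could have none. The pairing rule is not shown, nor is the direction or size of any effect on scores.

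**4. What a reverse-L1 group would give.** Let D = Spanish minus English, v the version effect and l the L1 effect. Then E(D) = v + l in Spanish-L1 participants and v − l in English-L1 participants. Hence l = (D̄₁ − D̄₂)/2 and v = (D̄₁ + D̄₂)/2, each with SE = ½√(1/n₁ + 1/n₂).

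With 19 + 6: SE = ½√(1/19 + 1/6) = 0.234, against 1/√19 = 0.229 for the planned contrast. With 23 df, power at l = 0.8 is 0.905 (0.904 with a term for order). One added participant already gives full rank, but power is only 0.31. Six is a power figure, not the threshold for estimability.

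**5. What that 0.90 rests on.**
- *The whole of d = 0.8 is L1 status.* The plan's 0.8 is for the L1–L2 contrast, which is v + l. If l is 0.6, 0.5 or 0.4, power at 19 + 6 is 0.69, 0.53 or 0.37.
- *The L1 effect is equal in both groups.* If it is l₁ and l₂, then (D̄₁ + D̄₂)/2 estimates v + (l₁ − l₂)/2. With v = 0, l₁ = 0.8 and l₂ = 0.2, the version estimate averages 0.30 SD and is declared significant about 23% of the time (simulation, 19 + 6).
- *Equal SDs.* If the SD is 1.5 times larger in the six, the equal-variance test has a type I error of about 0.11, and an unequal-variance (Welch) test has power of about 0.55. Six people are too few to check this.

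**6. Cost.** 25 instead of 19 participants: 6/19 = 32% more, all from a new population. Splitting a total of 20 as 10 + 10 would leave the Spanish-L1 contrast at power 0.62.

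**The case for a change.** The strongest case for acting is that readers will take a result labelled L1 versus L2 as a native-language effect, which this design cannot isolate at any sample size. The stated digit set differs in form between the two languages, and nothing in the text describes equating the versions. Six more participants would leave the planned 19 and their contrast intact and add an estimate the plan cannot otherwise give. Failing that, one sentence in Data Analysis would limit the attribution.

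The confounding stands, and so do the syllable counts if the Spanish recordings use the stated set. What does not stand is the step to a correction. The aim concerns the language of the materials, and no part of the document claims an effect of L1 status apart from the materials. The six-person group delivers the promised separation only under the conditions in step 5, and the documents do not show how easily English-L1 speakers scoring above 80% in Spanish could be found. The sentence would guard against a claim the plan does not make, and it adds no information. It is ordinary caution for whoever writes up the results.

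**Conclusion.** No change to the plan. L1 status and test version are fully confounded (rank 20 of 21), but the composite is the quantity the stated aim asks about: how Spanish-L1 bilinguals perform on these Spanish materials compared with these English ones. The study is sized correctly for it (0.909 at n = 19, taking d as the standardised paired difference). The result applies to that population and those versions, and should be read that way.

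A reverse-L1 group is an optional extension that answers a further question. It costs 32% more participants from a population of unknown availability. Its power for L1 status is about 0.90 at best and 0.53 if the L1 part of the effect is 0.5. It also relies on equal SDs and a common version effect, and a separate version estimate needs an equal L1 effect in both groups. Leaving it out is a fair trade-off.

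This judgement rests on the text available, in which only Spanish-L1 participants are described. If the demographic criteria, which were not available, also admit English-L1 bilinguals, the confounding would be partly broken already and the concern would be weaker still.

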## **Data Analysis**

Mixed linear regression models will be used to evaluate performance differences between L1 and L2 on APD assessments. Post-hoc adjustments will be used to correct for multiple comparisons. Correlations will also be conducted to investigate relationships between auditory processing performance and demographic variables including language proficiency.

Based on the proposed analyses, an a priori power analysis was conducted to estimate the required sample size. The power analysis (t-test estimates, 2-tailed,  $\alpha = 0.05$ , power = 0.90; G\*Power 3.1; Faul et al., 2007) revealed a sample size of 19 participants would be sufficient to detect large effect sizes ( $d = 0.8$ ), similar effects as reported in studies using similar paradigms (Desjardins et al., 2019; Lopez et al., 1997).

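### Does the mixed model need a stated error structure before its L1-L2 contrasts can be trusted at n = 19?

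*Combined protocol and SAP*

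**What the plan says.** The Study Protocol section states "The proposed study is a repeated measures experimental design": every participant takes three dichotic tests in Spanish and again in English. The tasks differ. For digits, "The participant will be asked to repeat all four numbers; the order of repetition is not important"; for sentences, "The participant is instructed to only repeat the sentence presented at the target ear", and the word test likewise asks for the target-ear word alone. The section refers to scoring sheets, but they are not in the text supplied, so the score scales are unknown.

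The Data Analysis section gives the comparison in one sentence, "Mixed linear regression models will be used to evaluate performance differences between L1 and L2 on APD assessments", and adds "Post-hoc adjustments will be used to correct for multiple comparisons". It does not say whether the tests enter one model or three, which random effects are used, whether residual variance may differ by test, or how degrees of freedom are obtained. The sample size of 19 is described as "t-test estimates, 2-tailed", with alpha 0.05, power 0.90 and d = 0.8.

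**The concern.** The sample size comes from a t-test and the analysis from a mixed model, and nothing written ties the second model's error term to the first. Scores on four recalled digits, one target word and one target sentence (presented 15 dB below its competitor, 35 against 50 dB SL) could well have different spreads.

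Suppose an analyst stacked all the scores, fitted a participant intercept with one residual variance, and took adjusted contrasts. All three language contrasts would then share one standard error. It would be too small for the most variable test (false positives) and too large for the least variable (lost power). If an overall language effect were also tested, and people differ in their L1-L2 gap, the several rows per language would count as independent evidence on that effect when they are not.

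**Working it through.** **1. Reproduce n = 19.** Inputs from Data Analysis: d = 0.8, two-sided alpha 0.05, power 0.90. For a paired t-test, df = n - 1 and the noncentrality is d × √n.
- n = 18: 0.8 × √18 = 3.394; critical t (17 df) 2.110; power 0.892.
- n = 19: 0.8 × √19 = 3.487; critical t (18 df) 2.101; power 0.909.

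The smallest n reaching 0.90 is 19, an exact match. A one-sided test would give 15, and a two-sample test 33 per group (normal approximation). The word paired is not in the text, but the figure implies it.

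**2. One model per test.** With one score per language, a random-intercept model has two rows per participant. The contrast variance is 2σ²/n. With complete data and a positive estimated participant variance, REML estimates σ² by half the variance of the paired difference. The standard error is therefore SD(difference)/√n, which is the paired t-test. In a simulated dataset of 19, the mixed-model t and the paired t (18 df) were both 2.122. Nothing is mismatched under this reading.

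**3. One pooled model, participant intercept only.** The documents give no SDs, so all SDs here and below are assumptions. Take difference SDs of 5, 10 and 15 points.
- Error variances (SD²/2): 12.5, 50, 112.5; mean 58.33.
- Shared standard error: √(2 × 58.33/19) = 2.48.
- Correct standard errors (SD/√19): 1.15, 2.29, 3.44.
- Pooled df: 5 × 18 = 90. Bonferroni level: 0.05/3 = 0.0167, critical t 2.44.
- For the third test, rejection needs only 2.44 × 2.48/3.44 = 1.76 true standard errors, a two-sided tail of about 8%.

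**4. Let people differ in relative ability across the tests.** A participant-by-test SD of τ raises the expected pooled residual variance by 0.8τ²: two of every five residual df belong to participant-by-test, each carrying 2τ², and 2 × 2/5 = 0.8.
- τ = 5: 58.33 + 20 = 78.33; shared standard error √(2 × 78.33/19) = 2.87.
- τ = 10: 58.33 + 80 = 138.33; shared standard error 3.82, now above all three correct values.

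Simulated rejection with no true effect (n = 19, 20,000 trials, nominal 1.67% per test and 5% family-wise):

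| Difference SDs | τ | Per test (%) | Family-wise (%) |
|---|---|---|---|
| 10/10/10 | 0 | 1.7 / 1.7 / 1.7 | 5.0 |
| 8/10/12 | 0 | 0.3 / 1.6 / 4.1 | 5.8 |
| 8/10/12 | 5 | 0.1 / 0.5 / 1.7 | 2.2 |
| 5/10/15 | 0 | 0.0 / 1.1 / 8.3 | 9.3 |
| 5/10/15 | 5 | 0.0 / 0.3 / 4.5 | 4.8 |
| 5/10/15 | 10 | 0.0 / 0.0 / 0.9 | 0.9 |

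Pooling can also cost power. With equal error SDs of 5 and τ = 5, per-test power at a standardised difference of 0.8 (unadjusted 0.05) falls from 0.91 to 0.79.

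**5. An overall language test.** With participant-by-language variance at an assumed 10% or 25% of the residual, a nominal 5% test rejects 11% or 19% of the time with six rows per language (three tests, two ears), and 8% or 11% with three rows. The plan specifies neither an overall test across tasks nor separate rows by ear.

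**The case for a change.** The strongest case for acting is that pooling is a permitted reading. The text allows a joint random-intercept fit, the choice could be made after seeing the data, and two sentences now would close it off at no cost. Some of the harm survives milder assumptions: with SDs of 8/10/12 and no participant-by-test variance, the most variable test still rejects at about 2.5 times its nominal level (4.1/1.67). People plausibly do differ in their L1-L2 gap, since the plan itself means to correlate performance with language proficiency.

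The point about pooled models stands: fitted with an intercept only, they can give wrong per-test standard errors. What does not stand is the step from there to a fault in this plan. The word models is plural, and nothing states a single model, an intercept-only random part or a common residual variance. Unequal score variances and separate ear rows are likewise inferred, not documented. The suggested fallback is also incomplete. A joint model with test-specific residual variances and a participant slope for language omits the participant-by-test term, and so would not by itself restore the paired comparison.

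**Conclusion.** No change follows. The plan leaves the model's structure open, and an analyst can fill it sensibly without departing from it: one model per test is compatible with the text and returns the paired comparison on 18 df for which 19 participants give power 0.909. That equivalence assumes complete data and one score per test and language. If ears gave several rows per language, ordinary practice would be to add a participant-by-language term, which the words mixed model already allow.

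The inflated error rates belong to a pooled fit that the plan does not specify. Under the assumed SDs tabulated above, family-wise error runs from 0.9% to 9.3% against 5%, so neither the size nor the direction of the harm can be read from the documents. The sample size is not affected for an unadjusted contrast on each test. Whether it should allow for the multiplicity adjustment is a separate matter.

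### The stated 0.90 power is for one uncorrected comparison and does not carry over to the individual auditory tests once the planned multiplicity correction is applied

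*Combined protocol and SAP*

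**What the plan says.** All of the statistical text is in the Data Analysis section. The main analysis is described as "Mixed linear regression models will be used to evaluate performance differences between L1 and L2 on APD assessments", followed by "Post-hoc adjustments will be used to correct for multiple comparisons". No correction method, family or number of comparisons is given, and no primary test, composite or contrast is named.

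The sizing is introduced with "Based on the proposed analyses, an a priori power analysis was conducted to estimate the required sample size". Its inputs are "t-test estimates, 2-tailed", alpha 0.05, power 0.90 and d = 0.8, and the conclusion is that it "revealed a sample size of 19 participants would be sufficient to detect large effect sizes". The 0.90 is not attached to any particular comparison.

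The Study Protocol section states that each participant is tested once in each language "using dichotic digits, competing words, and competing sentences", and gives the overall aim as "to determine if the language used in the test materials impacts auditory processing performance".

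**The concern.** The power analysis is presented as reflecting the proposed analyses. Those involve several auditory tests and a correction for multiplicity, yet the calculation uses the full alpha of 0.05 with no allowance for it. If the L1-L2 comparison on each test is in the corrected family, each faces a stricter threshold than the one used for sizing.

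This is the plan's only sample-size justification. A reader who takes 0.90 at face value would assume a 10% chance of missing a true d = 0.8 on a given test. If the real chance is higher, a non-significant result on one test is weaker evidence that test language makes no difference than the plan implies.

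**Working it through.** **Inputs from the Data Analysis section:** n = 19, d = 0.8, two-sided alpha 0.05, target power 0.90. **From the Study Protocol section:** within-participant design, three tests in two languages.

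**Assumptions not in the documents:** d is the mean paired difference divided by the SD of the differences; the family is the three per-test comparisons; the correction method; the correlation between the three paired differences; the form of the mixed model.

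**Step 1. Reproduce 19.** For a paired t-test, df = n − 1 and the noncentrality is d√n. Power = P(|T| > critical value), with T noncentral t.

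- n = 18: noncentrality 0.8 × √18 = 3.394, critical value 2.110, power 0.892.
- n = 19: noncentrality 0.8 × √19 = 3.487, critical value 2.101, power 0.909.

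So 19 is the smallest n reaching 0.90. Other set-ups do not give 19: a one-sided paired test needs 15, and a two-sample t-test needs 34 per group. The figure is one paired comparison at unadjusted alpha.

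**Step 2. Bonferroni over three, tests analysed separately.** Alpha per test = 0.05/3 = 0.0167.

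- n = 19: critical value 2.639, power 0.791. The effect detectable with 90% power rises from d = 0.79 (uncorrected) to d = 0.92.
- n = 24 gives 0.899 and n = 25 gives 0.913.

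**Step 3. Stepwise methods over the same three, n = 19.** Simulated power per test for the tests with a true d = 0.8:

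| Method | One effect real | Two real | Three real | Correlations |
|---|---|---|---|---|
| Holm | 0.79 | 0.82–0.83 | 0.85–0.89 | 0–0.8 |
| Hochberg | 0.79–0.80 | 0.83–0.84 | 0.88–0.90 (maximum 0.897) | 0–0.6 |
| Benjamini-Hochberg | 0.80 | 0.86 | 0.89–0.90 | 0–0.6 |

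Only Benjamini-Hochberg reaches 0.90, and only with all three effects real and correlation of about 0.1 or less.

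**Step 4. One pooled model.** Suppose one random-intercept model covers three tests by two languages with a common residual variance. Residual df = 6n − n − 5 = 5n − 5, which is 90 at n = 19. With the same noncentrality of 3.487 and alpha 0.05/3, the critical value is 2.440 and power is 0.850. In this model 22 participants give 0.904.

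**Step 5. Meanings of the 0.90 that are favourable to the plan, n = 19.**

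- *One overall language effect at alpha 0.05, with d = 0.8 defined on it:* 0.909, as in Step 1.
- *Average of the three paired differences (equal variances), m of the three at d = 0.8.* The effect size of the average is (0.8m/3) × √(3/(1 + 2ρ)). With m = 3 it is 1.386 at ρ = 0 and 0.859 at ρ = 0.8, so power runs from 1.00 down to 0.94. With m = 1 it is 0.462 and 0.286, so power runs from 0.48 down to 0.22.
- *At least one significant test under Bonferroni, all three at d = 0.8:* 0.99 at ρ = 0, falling to 0.90 at ρ = 0.8 (simulation).

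**The case against.** The strongest reply is that nothing here is contradictory. The announced adjustments are called post-hoc and come directly after the mixed-model sentence, so they can be read as applying only to follow-up contrasts. The Study Protocol section poses a single question about language. On that reading one overall effect is tested at 0.05 and needs no correction. If all three tests truly differ by d = 0.8, an averaged effect has power 0.94 to 1.00, and the chance of at least one significant test is 0.90 to 0.99 even after Bonferroni. In those cases 19 is enough or more than enough.

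This stands as far as it goes, and it limits the point. It does not remove it: the plan neither names an overall effect as primary nor says that the 0.90 refers to one, and under every one of these readings the corrected per-test results still have no stated power. The favourable averaged figure also depends on all three tests differing; if only one does, it drops to about 0.2 to 0.5.

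It is also fair to object that 0.79 is the result of one method and one model. The Holm and pooled-model figures are closer to 0.90, so 0.79 should be read as the low end for a family of three.

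A reader might infer that 19 is a miscalculation, or that the study is underpowered and must enrol 25. The documents support neither. The arithmetic for 19 is exact, and 25 follows only if 0.90 is wanted for each test under Bonferroni over three with separate paired analyses, none of which the plan states.

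**Conclusion.** The point holds in limited form. The sample-size calculation leaves out the correction that the same section announces, so the stated 0.90 cannot be taken as the power of the corrected comparison on each auditory test.

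For a family of three at n = 19 and d = 0.8, power per test is 0.79 under Bonferroni with separate analyses. Under Holm it is 0.79 with one real effect and about 0.85 to 0.89 with three. Bonferroni in one pooled model gives about 0.85. The corresponding chance of missing a true effect on a given test is thus about 11% to 21%, against the 10% that the plan implies. Benjamini-Hochberg can reach 0.90, but only in its most favourable setting.

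Confidence is high that the correction was omitted, because 19 is reproduced only at unadjusted alpha. Confidence is moderate on the size, which depends on a family, method, correlation and model that the plan does not give. Nothing here shows an inflated type I error, since correction is promised. The point should be fixed before analysis; it does not undermine the design.

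**What to change.** Restate the power in the Data Analysis section for the comparison that will actually be tested. Either option is enough:

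- **If the three tests are the corrected family:** name the family and method, and replace the 0.90 with the power per test at the corrected alpha. Suggested wording: *With Bonferroni or Holm correction over the three L1-L2 comparisons, analysed separately, 19 participants give at least about 79% power per test at d = 0.8.* Recompute the figure for the final model; a pooled random-intercept model would give a higher one.
- **If one comparison is primary:** name it (one test, or one overall language effect on which d = 0.8 is defined), test it at alpha 0.05, and state that the 0.90 applies to it alone and that the corrected per-test comparisons have lower power.

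The cost is one or two sentences and no added enrolment. The downside is a less favourable stated power under the first option, or advance commitment to one primary comparison under the second. Only if the sponsor chose to keep 0.90 for each test under Bonferroni over three, analysed separately, would enrolment rise, by 25 − 19 = 6 participants.
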